5.2. SAFETY ANALYSIS SET (SAF)

The safety analysis set (SAF) will contain all participants who are exposed to study intervention (either injection or ODT). Participants will be analyzed according to the treatment they actually received.

If there is any doubt whether a participant was treated or not, it will be assumed that the

Document: CCI

Author: PPD

Version Number:

3.0

Version Date:

19May2023

CCI

participant has been treated for the purposes of analysis.

When change from baseline is assessed, the participant will be included in the analysis only if the participant has a baseline and a postbaseline measurement.

6. GENERAL CONSIDERATIONS

6.1. REFERENCE START DATE AND STUDY DAY

Study Day will be calculated from the reference start date and will be used to show start/stop day of assessments and events. It will appear in every listing where an assessment date or event date appears. Reference start date is defined as the day of the first dose of study intervention.

Study day will be computed as follows:

Study Day = (Date of event – Date of first dose of study treatment) + 1 if the date of the event is on or after the date of the first dose of study treatment;

Study Day = (Date of event – Date of first dose of study treatment) if the date of the event is prior to the date of the first dose of study treatment;

where the event can be an adverse event, medical history event, start/end of concomitant medication, laboratory assessment, etc.

In the situation where the event date is partial or missing, the date will appear partial or missing in the listings.

For participants who are randomized but do not receive study treatment, study day will be calculated using the date of randomization as the reference start date.

6.2. BASELINE AND POST-BASELINE

Unless otherwise specified, baseline is defined as the last non-missing measurement taken prior to reference start date (including unscheduled assessments). If the time of the measurement is collected, both the date and time will be used to determine the baseline. For example, if assessments collected at Visit 1 to Visit 3 (prior to dosing at Visit 3, and this can be confirmed

Document: CCI

Author: PPD

Version Number:

3.0

Version Date:

19May2023

CCI

by time of the assessment and dosing time), the last non-missing measurement at Visit 3 prior to the first dosing will be counted as baseline. In the case where the last non-missing measurement and the reference start date coincide and the time is not collected, that measurement will be considered pre-baseline if the assessment is planned per protocol to take place prior to the first dose of study medication.

Vital Parameters (Pulse, SBP, and DBP) as these are captured in triplicates. Baseline and post-baseline will be the mean of the triplicate value. If only one value available then that value is used, if 2 values are available then the 2 values are averaged and used for the value at that visit.

Adverse Events (AEs) and medications commencing on the reference start date will be considered post-baseline unless otherwise indicated based on available start date/time combination or collected eCRF information that identifies the individual event/medication as starting prior to first study medication administration.

For treatment emergent abnormal laboratory or vital signs, the baseline criterion considers all predose records, instead of the last record only. That is

- A treatment-emergent abnormal result is defined as a change from normal at all predose/baseline visits to abnormal at any time during the treatment period. Patients with all normal values at predose/baseline will be included in the analysis of treatment-emergent abnormal laboratory values
- A treatment-emergent high result is defined as a change from a value less than or equal to the high limit at all predose/baseline visits to a value greater than the high limit at any time during the treatment period. Patients with all normal or low values at predose/baseline (no high values) will be included in the analysis of treatment-emergent high laboratory values.
- A treatment-emergent low result is defined as a change from a value greater than or equal to the low limit at all predose/baseline visits to a value less than the low. Patients with all normal or high values at predose/baseline (no low values) will be included in the analysis of treatment-emergent low laboratory values.

Baseline monthly migraine headache days value for primary efficacy analysis is calculated with a time window of 30 to 40 days (normalized to 30 days).

Document: **CCI**

Author: **PPD**

Version Number:

3.0

Version Date:

19May2023

CCI

Participant population with baseline and post-baseline definitions by type of analysis can be found in Table F:

Table F: Participant Population with Baseline and Post-Baseline Definitions by Type of Analysis

Analysis	Participant Population	Baseline Observation	Post-baseline Observation(s)
Primary/secondary/exploratory efficacy analyses (repeated measures or average of observed monthly values)	ITT Set with a baseline and at least one post-baseline observation	Visit 3	All scheduled visits 3<Visits ≤ 6
Primary/secondary/exploratory efficacy analyses	ITT Set with a baseline and at least one post-baseline observation	Visit 3	Last of Visit 3.01-6
Quality of Life analyses	ITT Set with a baseline and at least one post-baseline observation	Visit 3	All scheduled visits 3<Visits ≤ 6
TEAEs	Safety Analysis Set	All Visits 1-3	All Visits 3.01-6
Serious adverse events, discontinuations due to adverse events	Safety Analysis Set	NA	All Visits 3.01-6
Treatment emergent abnormal laboratory values	Safety Analysis Set with normal laboratory values at all non-missing baseline visits (with respect to direction being analyzed) and who have at least one post-baseline observation	Low: Minimum value from Visits 1-3 High: Maximum value from Visits 1-3	Low: Minimum value from Visits 3.01-6 High: Maximum value from Visits 3.01-6

Document: **CCI**

Author: **PPD**

Version Number:

3.0

Version Date:

19May2023

CCI

Analysis	Participant Population	Baseline Observation	Post-baseline Observation(s)
Treatment emergent changes in temperature	Safety Analysis Set with normal temperature values at all non-missing baseline visits (with respect to direction being analyzed) and who have at least one post-baseline observation	Low: Minimum value from Visits 1-3 High: Maximum value from Visits 1-3	Low: Minimum value from Visits 3.01-6 High: Maximum value from Visits 3.01-6
Treatment emergent changes in blood pressure (average of the triplicate value)	Safety Analysis Set with normal blood pressure values at all non-missing baseline visits (with respect to direction being analyzed) and who have at least one post-baseline observation	Low: Minimum value from Visits 1-3 High: Maximum value from Visits 1-3	Low: Minimum value from Visits 3.01-6 High: Maximum value from Visits 3.01-6
Treatment emergent changes in pulse (average of the triplicate value)	Safety Analysis Set with normal pulse values at all non-missing baseline visits (with respect to direction being analyzed) and who have at least one post-baseline observation	Low: Minimum value from Visits 1-3 High: Maximum value from Visits 1-3	Low: Minimum value from Visits 3.01-6 High: Maximum value from Visits 3.01-6

- Abbreviations: ITT = intent-to-treat; forward; NA = not applicable; TEAE = treatment-emergent adverse event.
- Note: Visit 3.01 indicates the first unscheduled visit occurring after Visit 3 and prior to Visit 4.

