### 7.1. Discontinuation of Study Intervention

In rare instances, it may be necessary for a participant to permanently discontinue study intervention. If study intervention is permanently discontinued, the participant should remain in the study to be evaluated for safety and efficacy assessments, unless criteria in Section [7.2](#) apply.

A participant should be permanently discontinued from study intervention if:

- the participant becomes pregnant during the study (see Section [8.3.2](#))
- the participant requests to discontinue study intervention
- clinical judgment of the investigator

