Objective	Estimands
	groups
Primary Sensitivity 1	
To assess whether galcanezumab is superior to rimegepant in the prevention of migraine in participants with episodic migraine	
Treatment condition: Galcanezumab injections of 120 mg SC or rimegepant 75 mg ODT regardless the use of acute medication to treat a migraine headache and regardless of discontinuing treatment due to any reason (treatment policy strategy)
 
Population: Participants who meet IHS-ICHD-3 (2018) criteria for a diagnosis of migraine with or without aura with an episodic frequency of 4 to 14 migraine headache days per month and fulfils the inclusion and exclusion criteria of the study.
 
Variable (endpoint): The percentage of participants with $\geq 50\%$ reduction from baseline in monthly migraine headache days across the 3-month double-blind treatment period
 
Remaining intercurrent event handling: The data after whichever of the following is sooner: the date of the last injection+30 days or the date of the last oral administration +1 day, will be discarded.
 
Summary measure: Difference of the overall mean monthly 50% response rate across the 3-month double-blind treatment period between treatment groups

Primary Sensitivity 2	
To assess whether galcanezumab is superior to rimegepant in the prevention of migraine in participants	
Treatment condition: Galcanezumab injections of 120 mg SC or rimegepant 75 mg ODT regardless of initiation of new preventive migraine medication, regardless the use of acute medication to treat an acute migraine attack and regardless of discontinuing treatment due to any reason (treatment policy strategy)

Document: CCI

Author: PPD

Version Number: 3.0

Version Date: 19May2023

Objective	Estimands
with episodic migraine	
Population: Participants who meet IHS-ICHD-3 (2018) criteria for a diagnosis of migraine with or without aura with an episodic frequency of 4 to 14 migraine headache days per month and fulfils the inclusion and exclusion criteria of the study.

	
Variable (endpoint): The percentage of participants with $\geq 50\%$ reduction from baseline in monthly migraine headache days across the 3-month double-blind treatment period

	
Remaining intercurrent event handling: The participants that withdraw for lack of efficacy or tolerability, or participants that initiate a new preventive treatment will be considered as non-responders (composite strategy)

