5.1. INTENTION TO TREAT (ITT) SET

The Intention to Treat (ITT) set will contain all randomized participants who receive at least 1 dose of both study interventions (injection and ODT). Participants will be included in the analyses according to their randomized treatment.

When change from baseline is assessed, the analysis will include participants in the ITT population who have a baseline and a postbaseline measurement.

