A 50% responder (Participant with $\geq 50\%$ reduction from baseline in migraine headache days): is defined as Yes, if any participant who has a $\geq 50\%$ reduction in the total number of migraine headache days in a 30-day period relative to baseline period, as No if otherwise. Therefore, if the percent change from baseline in the number of migraine headache days is $\geq 50\%$, the participant will be counted as an 50% responder.

Change from baseline in the number of monthly migraine headache days in each 30-day period will be summarized from daily data for each patient in that period (including approximately 30 days of daily data from the baseline period prior to randomization, 3 months of daily data during double-blind treatment period).

The daily ePRO data will reflect whether the patients meet the migraine / probable migraine criteria; those data will be aggregated, and the number of migraine headache days will be provided for each of the 30-day periods.

18.1.2. ADJUSTING FOR THE NUMBER OF DAYS WITH NON-MISSING DIARY DATA IN THE PERIOD:

In calculating the number of migraine headache days for each period, if the period is not equal to 30 days, the number of migraine headache days will be adjusted by multiplying the number of migraine headache days by $(30/x)$ where “x” is the total number of non-missing diary days in the period.

This approach to missing ePRO diary data assumes that the rate of migraine headaches per day is the same with missing and non-missing ePRO diary days, and it is missing at random. The same approach will also be applied to secondary and exploratory measures that are derived from the ePRO data.

Additionally, if the ePRO compliance rate (please refer to Section 17) for a monthly interval is $\leq 50\%$, then all endpoints to be derived from the ePRO diary data for that one-month period will be considered missing. For a participant who discontinued early in the double-blind treatment

Document: **CCI**

Author: **PPD**

Version Number:

3.0

Version Date:

19May2023

CCI

phase, compliance rate for the last month of that study period will be calculated with the denominator of the maximum of 30 and the total number of calendar days in that month.

Secondary and Exploratory Migraine and Headache Measures

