18.2.4. SENSITIVITY ANALYSIS OF PRIMARY EFFICACY VARIABLE(S)

The following sensitivity analyses are of the primary efficacy variable are planned:

- I) To consider the case where to discard the data of the participants that discontinue treatment and may have different expectations regarding efficacy of the two treatments such as the onset of effect given the different dosing and mode of administration of the comparators. For such analyses, the data after whichever of the following is sooner will be discarded: the date of the last injection+30 days or the

Document:

CCI

Author:

PPD

Version Number:

3.0

Version Date:

19May2023

date of the last oral administration +1 day.

- II) To consider participants that withdraw for lack of efficacy or tolerability, or participants that switch preventive treatment as no responders (composite strategy).
- III) To consider a migraine headache day when the participant takes acute medication regardless of the headache does not meet the criteria of migraine. This analysis will consider if a participant uses an acute medication (triptans or ergot derivatives) – as reported in the CRF (CM_AHM), regardless of whether a headache was reported. For this analysis baseline and post-baseline ‘migraine headache days’ need to be defined using the reporting of medications in CM_AHM CRF. Input from clinical will be used to help identify the classes of acute medication used.
- IV) To assess the robustness of the primary analysis conclusions to deviations from missing at random (MAR) assumption. The approach for these analyses is to vary the assumptions of missing data for the primary analysis in a systematic way. Basically, the method will be to predict the missing outcomes and then add values ($\Delta_{120}, \Delta_{75}$) to the predictions in the Galcanezumab 120 mg and rimegepant 75 mg treatment groups respectively, regardless of the reason the data are missing. This approach is consistent with the sensitivity approach suggested in Permutt (2015). This procedure will be repeated multiple times for different values of ($\Delta_{120}, \Delta_{75}$) using the following steps:
 - 1) Predict the missing outcomes for each treatment via multiple imputation based on observed primary endpoint and baseline values. Such imputation will be carried out using a Markov Chain Monte Carlo method with a Jeffreys prior via SAS® PROC MI. Thirty (30) such imputations will be created.

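### Table F's post-baseline condition, read with the 50% diary rule, conflicts with the composite sensitivity analysis on participants who withdraw in about the first two weeks

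*SAP*

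**What the plan says.** **Population.** Both efficacy rows of Table F (SAP 6.2) cover primary, secondary and exploratory efficacy analyses and give the population as "ITT Set with a baseline and at least one post-baseline observation". No sensitivity analysis is carved out. SAP 5.1 has a similar condition for change-from-baseline analyses: "the analysis will include participants in the ITT population who have a baseline and a postbaseline measurement".

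**ITT set.** SAP 5.1: "The Intention to Treat (ITT) set will contain all randomized participants who receive at least 1 dose of both study interventions (injection and ODT"). Both products are first given at Visit 3, so a participant who took both and left days later is in the ITT set.

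**When a diary month is missing.** Under SAP 18.1.2, if monthly diary compliance is 50% or lower, "then all endpoints to be derived from the ePRO diary data for that one-month period will be considered missing". For a participant who stops early in the double-blind phase, the "compliance rate for the last month of that study period will be calculated with the denominator of the maximum of 30" and the calendar days in that month.

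**Composite analysis.** Table E (SAP 2.4), Primary Sensitivity 2: "The participants that withdraw for lack of efficacy or tolerability, or participants that initiate a new preventive treatment will be considered as non-responders". SAP 18.2.4 item II repeats the rule: "To consider participants that withdraw for lack of efficacy or tolerability, or participants that switch preventive treatment as no responders (composite strategy"). Neither place sets a minimum time in study, and the Table E population for this analysis has no post-baseline condition. This analysis is called Sensitivity II below.

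**The concern.** In a composite strategy the intercurrent event is itself the outcome. A participant who withdraws on day 10 because of intolerance is a non-responder by definition, and no diary month is needed to establish that. Table F and the 50% rule together point the other way: with no evaluable month there is no responder value, so the participant falls outside the population. Late withdrawals would then count as failures while the earliest ones disappear.

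Sensitivity II is a named, pre-specified check on the primary result. If early leavers are dropped, the composite response rate is too high in any arm that has them, and the treatment difference is distorted when the arms differ in early withdrawal. Two competent programmers could follow the same SAP and report different results.

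Sensitivity IV has a related gap. Its imputation uses the observed endpoint together with baseline values and applies the shift whatever the cause of missingness, so it could cover baseline-only participants. Table F would exclude them.

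**Working it through.** **Plan's own figure.** The SAP gives no figure for Sensitivity II. SAP 3.1.1 gives a 12-point difference, about 575 randomized, more than 85% power and dropout of at most 10%. The power figure cannot be confirmed, because response rates and within-participant correlation are withheld. With one binary outcome and a rimegepant rate of 35% to 55%, power is 82–84% at N = 575 and 78–80% at N = 517.5 (575 × 0.9). Averaging three months at correlation 0.7, with a rimegepant rate of 40% to 50%, gives 86–87% at N = 517.5. The stated power is therefore attainable and is not in question here. Only the 12 points are carried forward.

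**Step 1: the cut-off (SAP 18.1.2).** Compliance = completed diary days / max(30, calendar days in the month).
- 15/30 = 50.0%: missing.
- 16/30 = 53.3%: kept.

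A participant who leaves with 15 or fewer completed Month 1 diary days has no monthly responder value. That is about two weeks with a full diary. At 80% completion it reaches about day 18 (15/0.8 = 18.75).

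**Step 2: the provisions side by side.**

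| Provision | Early leaver, qualifying reason, no evaluable month |
|---|---|
| SAP 5.1, ITT set | Included, if both products were taken |
| SAP 6.2, Table F, read literally | Excluded |
| SAP 2.4, Table E, Primary Sensitivity 2 | Non-responder |
| SAP 18.2.4 II | Non-responder |

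The SAP does not say whether an assigned non-response counts as a post-baseline observation, which months receive it, or which provision prevails.

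**Step 3: illustrative size.** Let p be the response rate among evaluable participants and e the share of an arm that leaves for a qualifying reason before Month 1 is evaluable. If those leavers are non-responders in every month:

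D = pG(1 − eG) − pR(1 − eR)

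Dropping them gives D = pG − pR = 12.0 points. The documents give neither p nor e, so these are assumptions: pG = 62%, pR = 50%.

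| eG | eR | Calculation | D (points) | Shift |
|---|---|---|---|---|
| 2% | 2% | 62 × 0.98 − 50 × 0.98 | 11.76 | −0.24 |
| 3% | 1% | 62 × 0.97 − 50 × 0.99 | 10.64 | −1.36 |
| 1% | 3% | 62 × 0.99 − 50 × 0.97 | 12.88 | +0.88 |

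With pR = 40% and pG = 52%, the same rows give 11.76, 10.84 and 12.68. At 5% in both arms, D is 11.4. In the extreme case of 5% in one arm and none in the other, across both sets of response rates, D is 8.9 to 9.4 if the leavers are on galcanezumab and 14.0 to 14.5 if they are on rimegepant.

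With about 287 per arm, 1% is about 3 participants, 3% about 9 and 5% about 14. The 10% dropout allowance is at most about 58 participants in total, for all reasons and times.

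**The case against.** The strongest reply is that the specific instruction governs. Table E and 18.2.4 II call these withdrawers non-responders without qualification. Table F is a general table that does not mention sensitivity analyses, define an observation as an evaluable diary month, or say that an assigned outcome fails to count. A programmer working from 18.2.4 II could well code them as failures. This is a fair reading, and it means that exclusion is not settled. It does not remove the conflict: Table F exempts nothing, and Table E attaches a population note to Primary Sensitivity 3 but none to Primary Sensitivity 2.

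Four further limits stand.
- A reader might infer that early leavers vanish from every efficacy analysis. They do not necessarily: the 50% rule covers diary endpoints only, and MSQ, MIDAS and PGI-S are scheduled at early termination.
- Stopping drug is not leaving the study. Protocol 7.1 says that "the participant should remain in the study to be evaluated for safety and efficacy assessments" unless a study-withdrawal criterion applies, and the SAP uses those data. The point concerns participants who leave the study or stop the diary.
- A reader might suppose that the earliest leavers are the likeliest to have left over tolerability. This is plausible, but the documents do not say it.
- The withdrawal rates above are assumed. Protocol 7.2 expects discontinuation to be uncommon, and with equal rates the shift is small.

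**Conclusion.** The conflict is real and should be resolved. Applied literally, Table F with the 50% rule removes from Sensitivity II participants whom its estimand counts as non-responders. The documents do not support the stronger conclusion that Sensitivity II definitely fails to estimate its stated estimand, because 2.4 and 18.2.4 II can be read as overriding Table F.

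The primary test is unaffected: a participant with no monthly value adds nothing to the primary GLIMMIX, with or without Table F. The key secondary hierarchy is also unaffected.

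Under the assumed rates, the shift is about a quarter of a point at an equal 2% and about 1 point when the arms differ by 2 percentage points in early withdrawal. The largest of the 1%-to-3% cases is 1.36/12 = 11% of the planned difference. This assumes a 12-point difference among evaluable participants, that all early leavers counted in e left for a qualifying reason, and that they are non-responders in every month. The actual size depends on early-withdrawal rates that the documents do not give.

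**What to change.** - **SAP 18.2.4 II and a Table F footnote:** state that Sensitivity II includes all ITT participants with a baseline and that Table F's post-baseline condition does not apply. A qualifying withdrawal or start of a new preventive is non-response for at least every month without a valid value, even when no post-baseline month is evaluable.
- **Valid months before the event:** pre-specify before unblinding whether they keep their observed value or become non-response. The SAP is silent. Overwriting them is a debatable choice and should not be made by default.
- **SAP 18.2.4 IV:** state that the imputation also covers ITT participants with a baseline but no evaluable month.
- **Reporting:** tabulate by arm the number with no evaluable month and the reason.

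The cost is a few sentences, a footnote and one small table. No new data are needed, since SAP 9.1 already tabulates discontinuation and its reasons for ITT participants. Composite response rates may come out slightly lower. SAP 5 already requires inclusion and exclusion to be agreed before unblinding, which is the natural time to settle this.
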